**II. Purpose:**

Our overall aim of this study is to perform a randomized clinical trial (RCT) in a diverse, largely minority, cross-section of at least 2,000 US residents to test the hypothesis that vitamin D supplementation with 4,000 IU/day compared to minimal supplementation with 400 IU/day will decrease COVID-19 incidence (primary outcome) and adverse health outcomes (secondary outcome).

Primary Outcome: patient report of lab-confirmed COVID-19 (and date). Secondary Outcomes: patient report of hospitalization (and date), ICU use, mechanical ventilation, death, patient-reported adherence to vitamin D supplementation, and results of COVID-19 antibody blood spot tests. Key milestones for success will include partner and participant recruitment, including intake surveys, baseline Vitamin D levels and antibody testing for 20% of the sample, vitamin D distribution to the participants, completion of quarterly surveys, end-of-study antibody testing for full sample, and analysis and publication of the study results.

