A minimum of 2,000 eligible participants will be randomized to the 400 IU/day or 4,000 IU/day treatment arms. Each lot of vitamin D supplements will be tested to ensure they are within the dosing tolerance that meets USP standards. Transitional participants will maintain their dosing arm from the previous NIH study; those in the high or moderate dosing arms (10,000 IU/day or 4,000 IU/day) will receive 4,000 IU/day and those who were previously in the low arm (400 IU/day) will receive 400 IU/day. The UCM pharmacy will prepare and package blind-label safety-top medication bottles to be distributed to participants via mail to either their home address or for pick-up from community partners. During the 12-month implementation period, we will ask participants to complete follow-up surveys every 3 months. A sample of the participants (20%) who complete the surveys also have the opportunity to receive a free home COVID-19 antibody blood spot test and Vitamin D level tests at the beginning of the study. Both tests are done at home by the participant themselves. Testing this subset will allow the research team to capture baseline levels of Vitamin D and immunity to COVID-19. We suspect 10% will have positive antibodies and 80-90% will be Vitamin D deficient; these baseline sample tests will confirm the general hypothesis. Originally, we planned for the entire sample to be offered the opportunity to receive a free, in home COVID-19 antibody blood spot tests at the end of the study. Due to low return rate, we paused end of study testing in early 2024 and now wish to permanently discontinue it. Over the course of this three year study, it is likely that most participants have COVID-19 antibodies, therefore testing is no longer scientifically valuable. Results of the antibody test will help inform research outcomes and may increase completion of quarterly self-reported surveys.

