In addition to these questions, we have added some questions on the baseline and follow-up surveys that evaluate sleep habits as well as additional possible risk factors for COVID-19 outcomes. These risk factors—hypertension, diabetes, and mood—are shown to have possible linkages to vitamin D levels. These factors are receiving increased attention in the context of COVID-19 risk and its relationship to low vitamin D levels. While available evidence suggests there is a link between hypertension/cardiovascular disease, diabetes and metabolism, depression/anxiety, and vitamin D levels, to-date no causal relationship has been established. This is supported by both evidence as recently as this year, as well as earlier studies. Questions about hypertension and diabetes are of our own construction, and questions about depression and anxiety come from validated instruments, the GAD-2 and the PHQ-2. We hope to shed light on the relationship between our outcomes of interest, vitamin D, and these risk factors by asking subjects, both already enrolled and new, about these factors.

Our data management plan will specify procedures to collect, organize, handle, clean, analyze, describe, preserve, destroy, report and share data. We will review self-reported survey data regularly to prevent and monitor missing data. We will record and report all known reasons for study dropout and missing data. For our primary outcome of COVID-19 infection as measured by patient report of clinically confirmed COVID-19 (or viral PCR if available) and COVID-19 seroconversion tests that data collection, hazard models will be used to assess the effect of vitamin D dosing on the outcome. We will first develop hazard ratios for between-group analyses on the primary outcome using log-rank tests, and then Cox proportional hazard models with covariates including vitamin D dose, age, gender, race, ethnicity, sun exposure, exposure of cohabitants,

employment status, and geographic location. Secondary study outcomes of hospitalization, ICU use, mechanical ventilation use and death will be analyzed with longitudinal mixed models with these covariates.

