We estimate statistical power using a simulation model based on conservative estimates of the fraction of Chicagoans already immune but unaware they have had COVID-19 ( $\leq 10\%$ ), monthly incidence of COVID-19 (3%/month for Black and Latinx persons and 1%/month for White persons), size of the true effect of vitamin D on incidence we seek to assess, confidence we wish in that assessment, and length of time participants are followed. Based on this we propose to recruit at least 2,000 participants, yielding 80% power at  $p < 0.05$  to demonstrate a reduction of 20% or more in COVID-19 incidence due to vitamin D within 12 months of randomization.

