## **IX. Description of statistical analysis**

The higher doses we propose, 4,000 IU/d is expected to maximize the vitamin D treatment effect if one exists compared to a lower high dose as in a Harvard study currently underway which explores 2,000IU/day vitamin D. While the Harvard study gives vitamin D in the context of acute infection or household exposure so vitamin D levels may not respond quickly enough to affect outcomes (perhaps both for treatment and prevention), our proposed design seeks to raise vitamin D levels in advance of sustained risk in community members who are disproportionately at increased risk of COVID-19, increasing the underlying risk of COVID-19 that increases the expected treatment effect, and therefore increases overall statistical power.

For our primary outcome of COVID-19 infection as measured by patient report of clinically confirmed COVID-19 (or viral PCR when available) and secondary outcomes of COVID-19 antibody seroconversion and disease severity (hospitalization, ICU stay, ventilator use, death), hazard models will be employed to assess the effect of each vitamin D dosing strategy on the outcome. We will first develop hazard ratios for between-group analyses on the primary outcome using log-rank tests, and then develop Cox proportional hazard models to model the hazard function on a set of covariates including but not limited to vitamin D dose, baseline vitamin D levels, age, gender, race, ethnicity, sun exposure, sleep habits, exposure of cohabitants, job type, and study site. We will also control for randomization date to adjust the underlying hazard function for COVID-19 prevalence over time. As noted above, we estimate statistical power using a simulation model based on conservative estimates of the fraction of Chicagoans already immune but unaware they have had COVID-19 ( $\leq 10\%$ ), monthly incidence of COVID-19 (3%/month for Black/Latinx persons and 1%/month for White persons), size of the true effect of vitamin D on incidence we seek to assess, confidence we wish in that assessment, and length of time participants are followed. Based on this we propose to recruit at least 2,000 participants, yielding 80% power at  $p < 0.05$  to demonstrate a reduction of 20% or more in COVID-19 incidence due to vitamin D within 12 months of randomization.

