Primary analysis: We will use a multivariable Cox proportional hazards regression model to estimate an adjusted hazard ratio of the effect of moderate versus low dose vitamin D on the outcome. Covariates will include age, sex, race and ethnicity, baseline sun exposure, baseline insomnia severity, baseline COVID-19 exposure outside work, baseline employment, randomization date, and baseline geographic location. The selection and coding of these covariates mirror a prior NIH-funded trial of vitamin D and COVID-19 (NCT04868903). Coding of these covariates include age (continuous), sex (male versus female), race and ethnicity (non-Hispanic White versus non-White or Hispanic), sun exposure (average \leq 30 minutes per day versus $>$ 30 minutes per day), insomnia severity (no or subthreshold insomnia versus moderate or severe insomnia), COVID-19 exposure outside work (no versus yes), and employment (no versus yes). Non-Hispanic White participants will be defined as those who report White race and non-Hispanic or Latino ethnicity. Non-White or Hispanic participants will be defined as those who report either non-White race or Hispanic or Latino ethnicity. Whereas recruitment in the NIH trial was limited to Chicagoland and stratified by recruitment site (UChicago Medicine and Rush University Medical Center), this study recruited participants across the United States, such that we will include baseline geographic location as a covariate, defined by baseline mailing address latitude $<$ 40.0 or \geq 40.0 degrees. Furthermore, whereas the NIH trial recruited participants who concluded their participation prior to when Omicron arrived in Chicago about December 1, 2021, every participant in this study could be active in the study after Omicron arrived in the United States about December 1, 2021. Rather than control for randomization date with a linear time trend and an indicator variable for potential participation after Omicron arrived like the NIH trial, we will control for randomization date with a series of thirteen quarters defined by calendar quarter and year (Q1 2021 [December 2020 through March 2021], Q2 2021 [April 2021 through June 2021], Q3 2021 [July 2021 through September 2021], Q4 2021 [October 2021 through December 2021], Q1 2022 [January 2022 through March 2022], etc. up to Q1 2024 [January 2024 through April 2024]).

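### The 80% power for a 20% reduction is stated without racial mix, effect scale, sidedness or loss, and for the planned hazard ratio at two-sided 0.05 the stated inputs give 54-71%, at most 75%

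*Protocol*

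**What the plan says.** Protocol Section III says that a simulation led to the sample size: "Based on this we propose to recruit at least 2,000 participants, yielding 80% power at" p<0.05. Section IX repeats the claim and describes the target as "to demonstrate a reduction of 20% or more in COVID-19 incidence due to vitamin D within 12 months of randomization".

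The listed inputs are an immune-but-unaware fraction of at most 10%, monthly incidence ("3%/month for Black and Latinx persons and 1%/month for White persons"), an effect size, a confidence level and the length of follow-up. Neither section gives the Black/Latinx share, says whether the 20% is a reduction in hazard or in 12-month risk, says whether the test is one- or two-sided, allows for loss, or gives an expected event count. The SAP has no power or event-count statement, and its significance rule is p<0.05 without sidedness.

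The analysis scale is clear. Section III says "We will first develop hazard ratios for between-group analyses on the primary outcome using log-rank tests", followed by Cox models. The SAP's primary analysis is a Cox model "to estimate an adjusted hazard ratio of the effect of moderate versus low dose vitamin D on the outcome". Success Measure 3 in Section IV also names the hazard.

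On the mix, Section II says only that recruitment will be "in a diverse, largely minority, cross-section of at least 2,000 US residents".

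**The concern.** The two assumed incidence rates differ threefold, so the number of events, and with it the power, depends heavily on a Black/Latinx share that is not stated. The scale matters too. Over 12 months at these rates a 20% reduction in cumulative risk corresponds to a hazard ratio of about 0.77, a larger effect than a hazard ratio of 0.80.

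What is at stake is how the trial is read. At 80% power a true effect of the target size is missed in 2 of 10 such trials. If power is 54-71%, a true hazard ratio of 0.80 is missed in about 3 to 5 of 10. A null result should be read from its confidence interval, and actual incidence may differ from planning. But anyone who cites the design power beside a null hazard ratio would be relying on a figure that they cannot check.

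**Working it through.** **Inputs from the protocol:** 2,000 participants, half per arm (Section VII); 12 months of follow-up (Section IV); monthly incidence 3% or 1%; immune fraction 0 to 10%, the top being the protocol's upper bound.

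**Assumed, because not stated:** Black/Latinx share m from 50% to 100%; two-sided 0.05 unless noted; no loss unless noted; monthly rates compounding, since the SAP endpoint is first infection. Two-thirds is used as an illustration only: Section III gives Black and Latinx residents as about one third each of Chicago's population, but does not tie this to the power model.

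**1. Can the plan's own figure be reproduced?** Not uniquely. A close match is a two-sided comparison of 12-month risks, everyone Black/Latinx, 10% immune, no loss. Control risk is 0.9 × (1 − 0.97^12) = 27.6%, against 0.8 × 27.6% = 22.0%. The two-proportion formula then needs N = 1,926 for 80% power, or 1,998 with continuity correction.

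**2. Events needed for a hazard ratio of 0.80 (Schoenfeld).**
4 × (1.960 + 0.8416)² / (ln 0.80)² = 630.5, so 631.

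**3. Events expected, no loss.**
- Low-dose arm: 1,000 × (1 − immune) × [m(1 − 0.97^12) + (1 − m)(1 − 0.99^12)], where the bracketed risks are 0.3062 and 0.1136.
- Moderate-dose arm at hazard ratio 0.80: the exponent 12 becomes 9.6, and the risks are 0.2535 and 0.0920.
- Example (two-thirds, 10% immune): 217.8 + 179.7 = 397.5.

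**4. Power** = Φ(√(D/4) × |ln 0.80| − 1.960), D being total events. Example: √(397.5/4) × 0.2231 − 1.960 = 0.264, so Φ = 60%.

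| Black/Latinx share | Immune | Events | Power, HR 0.80 |
|---|---|---|---|
| 50% | 10% | 344 | 54% |
| two-thirds | 10% | 397 | 60% |
| 80% | 10% | 440 | 65% |
| 100% | 10% | 504 | 71% |
| 100% | 0% | 560 | 75% |

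A simulated log-rank test stratified by race (10,000 trials per setting, Monte Carlo error about 0.5 points) gives 53%, 59%, 63%, 69% and 75% for the same rows.

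**5. Other readings, no loss.** The share is the Black/Latinx share from which power reaches 80%. Ranges for the risk ratio span the event-based and two-proportion formulas.
- Two-sided, 12-month risk ratio 0.80: about 75-80% if nobody is immune; about 88-96% if 10% are.
- One-sided 0.05, hazard ratio 0.80 (497 events needed): about 82-83% if nobody is immune; about 98% if 10% are.
- One-sided 0.05, risk ratio 0.80, two-thirds Black/Latinx, 10% immune: power is about 79-82%.
- Two-sided, hazard ratio 0.80, crude accumulation of 12 × the monthly rate (36% and 12%), nobody immune: about 96%. There the events are 1,000 × 1.8 × (0.96 × 0.36 + 0.04 × 0.12) = 631.

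**6. Effect of loss (assumption).** Suppose 20% are censored by month 12 at a constant rate d = −ln(0.8)/12. This value is borrowed from the 80% follow-up criterion in Section IV, which is a success threshold and not a planning input. Events per arm become 1,000 × (1 − immune) × Σ w·λ/(λ+d) × [1 − exp(−12(λ+d))], where w is the group share and λ = −ln(1 − monthly rate), multiplied by 0.80 in the moderate arm. At two-thirds and 10% immune this gives about 358 events and 56% power. The hazard ratio detectable with 80% power is exp(−2 × 2.80/√358) = 0.74.

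**The case against.** The strongest reply is that 80% is reachable under choices that the documents leave open. The target wording in Section IX fits a 12-month risk ratio as well as a hazard ratio. On that scale, with nobody immune, a share of about 75-80% is enough, which is compatible with a largely minority sample. No passage says two-sided, and a one-sided risk-ratio reading reaches about 80% even at two-thirds Black/Latinx with 10% immune.

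Nor is immunity fixed at 10%. Section III gives that as an upper bound. Its separate expectation ("We suspect 10% will have positive antibodies and 80-90% will be Vitamin D deficient") concerns antibodies, and Section VIII says that it is not known whether a positive result relates to immunity.

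All of this stands. A reader might infer from the table that the simulation was run wrongly, or that no reading of the plan gives 80%. The documents support neither: several readings give 80%, and the simulation's settings are not reported.

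What the reply does not rescue is the figure as it will be used. The planned test is log-rank/Cox. With compounded rates and two-sided 0.05, no mix and no immune fraction from 0 to 10% gives 80% for a hazard ratio of 0.80. The crude 12 × rate exception needs nobody immune and a share of about 96%, and it applies the monthly rate to people already infected although the endpoint is first infection.

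It can also be said that recruitment is probably over, since the SAP's randomization quarters end in early 2024. That rules out a larger sample, not a correct statement of the power.

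**Conclusion.** The point holds in a conditional form. The power statement omits the Black/Latinx share, effect scale, sidedness and loss, and so cannot be checked. For the planned analysis at two-sided 0.05, with compounded monthly rates, 1:1 allocation and no loss, power for a hazard ratio of 0.80 is 54-71% with 10% immune and 50-100% Black/Latinx, and at most 75% in the most favourable case. A share below 50%, or any loss, lowers these figures.

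This is an under-specified figure that does not hold on the analysis scale at the conventional level. It is not a demonstrated error of calculation, and it does not bear on the validity of the test or the estimand. It should be fixed, because the correction is cheap and the figure will be cited.

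**What to change.** In Protocol Sections III and IX, replace the power sentence with one of this form:

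*The simulation assumed [x]% Black/Latinx participants, [y]% immune, [z]% loss by month 12, a 20% reduction in [hazard / 12-month risk] and a [two/one]-sided test at 0.05. For the planned log-rank/Cox analysis, 2,000 participants at these inputs give about [E] events, [p]% power for a hazard ratio of 0.80, and 80% power for a hazard ratio of [h].*

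As an illustration with assumed values, two-thirds Black/Latinx, 10% immune, 20% loss and a two-sided test would fill the last three blanks with about 358 events, 56% and about 0.74. If a 12-month risk ratio or a one-sided test underlies the 80%, say so and show that figure beside the hazard-ratio one.

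The cost is a text change, and the stated power becomes less favourable. No participants are added, and the test, the estimand and the blinding are unaffected.

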#### **IV. Probable duration:**

The study period, including recruitment, enrollment, and analysis, will last 36 months. We expect the recruitment period to last 18 months to enroll our target of 2,000 subjects. Once enrolled, subjects' participation will last 12 months total. This includes 12 months of taking a daily dose of vitamin D, answering surveys, analysis to measure outcomes.

*Recruitment: December 1, 2020 – February 29, 2023*

Research Objective(s) to be achieved: Obtain IRB approval, launch project website, recruit 5-10 community partner organizations to be able to help recruit a total of 2000 participants, recruit 2000 participants with target of completing all recruitment by mid 2022. Complete enrollment, consent and baseline survey and distribute Vitamin D to all participants' homes or other locations at the participant's choosing. Consent at least 20% of sample (200 in treatment arm; 200 in control arm) to complete baseline Vitamin D level tests and baseline antibody tests; mail out at-home testing to consented participants within the first two quarters of the study.

*Follow Up, Safety Monitoring and Analysis: March 1, 2021 – February 29, 2025*

Research Objective(s) to be achieved: Complete four quarterly follow-up survey. Begin analysis of data.

*Project Close: December 31, 2025*

Endpoint/Success Measure 1: Successful recruitment of 2000 subjects

Endpoint/Success Measure 2: Successful follow up of at least 80% of subjects to end of study period or study outcome of patient report of clinically confirmed COVID-19, with no difference in follow up rates between arms. Successful testing of COVID-19 antibodies of at least 80% of subjects.

Endpoint/Success Measure 3: Valid assessment of statistical significance of difference in COVID-19 risk (hazard) between treatment and control groups.

Endpoint/Success Measure 4: Collect, analyze and report Vitamin D levels for at least 80% of the 20% of the sample that will receive at-home test kits. We will work closely with the VitD testing distributor (Everlywell) to ensure compliance and test completion among participants and will use text and call reminders if needed.

#### **V. Location of research**

The research will take place at the University of Chicago Health Lab. Participants will be recruited through emails and flyers from partner organizations asking for their participation in the study. The recruitment materials will vary by partner, but we will submit an amendment with the final materials used. Actual study recruitment and follow-up processes will be conducted completely online to minimize exposure to COVID-19. Community partners will focus on communicating information about the study and distributing vitamin D supplements if needed. Expected organizational partners currently include Ingalls Hospital, St. Anthony Hospital, Heartland Health, the Greater Chicago Food Depository, and the YWCA. Subjects will be recruited from all of these specified locations via promotional materials.

The UCM pharmacy will prepare and package blind-label safety-top medication bottles to be distributed to participants via mail to a home address or to be picked-up from community partners. For transitional participants, the pharmacy will maintain the previous dosing arm from the NIH study. Those in the high or moderate dosing arms (10,000 IU/day or 4,000 IU/day) will receive 4,000 IU/day and those who were previously in the low arm (400 IU/day) will receive 400 IU/day. Each bottle will contain a 12-month supply of vitamin D tablets.

For 20% of the subjects, blood samples to test for Vitamin D levels and COVID-19 antibodies will be obtained at the beginning of the study by two different vendors: Everlywell and Rush Hospital. Originally, the entire study sample was offered antibody testing at the end of the study. We paused end of study antibody testing in early 2024 due to low return rate and now wish to permanently discontinue it. Over the course of this three year study, it is likely that most participants have COVID-19 antibodies, therefore testing is no longer scientifically valuable. The vitamin D test is a standard commercially available vitamin D home test and provides a number level measured in ng/ml. We currently plan to source this from Everlywell (<https://www.everlywell.com>). We will register vitamin D test kits with Everlywell on each subject's behalf, using subject's name and the test kit ID. Our current plan for the antibody test is to use the 'Rush Covid-19 Multi-analyte Serological Assay', which evaluates an immune response to four SARS-CoV-2 antigens, including the spike S1, nucleocapsid, matrix, and envelope glycoproteins in individuals convalescing from Covid-19. This assay has been developed by [name] at Rush and is built on the Luminex immunobead platform and was specifically engineered to provide greater confidence in diagnostic results through the use of an algorithm integrating results from the four independent assay findings and requires no less than two analytical findings to deliver a diagnostic result to significantly reduce the rate of 'False Negative' misclassifications. The analytical performance characteristics of the Rush Covid-19 Multianalyte Serological Assay have been calculated to be 100% sensitivity and 99.6% specificity with a 99.62% accuracy when evaluated against 44 cases with clinically-diagnosed Covid-19 within a window of 8 and 30 days from testing and 998 cases of pre-Covid-19 era (i.e. prior to 6/2019) specimens. This assay will be performed in [name] Development Facility, which falls under Rush Pathology's CLIA license. Both the Vitamin D and antibody blood tests will be self-administered, at-home, with no in-person contact, and will be mailed back to the vendors.

Survey data will be collected quarterly by the study team via a HIPAA-secure Redcap survey. Data will be stored on encrypted-password protected computers, locked filing cabinets, and secured encrypted drives in these offices.

